3. ENDPOINTS AND BASELINE VARIABLES: DEFINITIONS AND CONVENTIONS

Percent change from baseline will be calculated at the participant level = [(Post baseline value – Baseline)/Baseline] * 100%

3.1. Primary Endpoint

The primary efficacy evaluation will be the percent change in spleen volume (expressed in MN) measured by MRI from baseline to Month 12.

Spleen volume will be measured at the Screening and Month 12 according to the Schedule of Activities in Section 9 of the protocol, measured by MRI by site according to the Appendix 4 of the protocol. The spleen volume (cm^3) will be used for the sponsor to calculate the spleen volume by multiples of normal (MN) data applying the formula below:

$$\text{Spleen Volume by MN} = \frac{\text{Spleen Volume}}{2\text{cm}^3 / \text{kg} * \text{body weight}}$$

When body weight (kg) is not available at a visit, the body weight measured in the previous visit will be used to estimate the participant's expected normal volume at the visit.

3.2. Secondary Endpoint(s)

3.2.1. Liver Volume by MN

The secondary efficacy evaluation will be the percent change in liver volume (expressed in MN) measured by MRI from baseline to Month 12.

Liver volume will be measured at the Screening and Month 12 according to the Schedule of Activities in Section 9 of the protocol, measured by MRI by site according to the Appendix 4 of the protocol. The spleen volume (cm^3) will be used for the sponsor to calculate the liver volume by multiples of normal (MN) data applying the formula below:

$$\text{Liver Volume by MN} = \frac{\text{Liver Volume}}{25\text{cm}^3 / \text{kg} * \text{body weight}}$$

When body weight (kg) is not available at a visit, the body weight measured in the previous visit will be used to estimate the participant's expected normal volume at the visit.

3.2.2. Hemoglobin (g/dL)

Hemoglobin will be measured at Screening, Baseline, Month 3, Month 6, Month 9 and Month 12 according to the Schedule of Activities in Section 9 of the protocol.

3.2.3. Platelet Count ($10^3/\mu\text{L}$)

Platelets will be counted at Screening, Baseline, Month 3, Month 6, Month 9 and Month 12 according to the Schedule of Activities in Section 9 of the protocol.

3.2.4. Lyso-Gb1 Biomarker (ng/mL)

Lyso-Gb1 (lyso-glucosylsphingosine) will be measured at Baseline, Month 3, Month 6, Month 9 and Month 12 according to the Schedule of Activities in Section 9 of the protocol.

3.2.5. Chitotriosidase (nmol/ml/hr)

Chitotriosidase will be measured at Baseline, Month 3, Month 6, Month 9 and Month 12 at the same schedule of the biomarker of Lyso-Gb1 according to the Schedule of Activities in Section 9 of the protocol.

3.3. Other Endpoint(s)

3.3.1. Height SDS and Weight SDS

For change in growth and development, the height and weight will be assigned to a SDS/Z-scores using the World Health Organization (WHO) Child Growth Standards. The Center for Disease Control and Prevention (CDC) reference standards will be used for the age categories where the WHO reference standards are not available.

Height and weight will be collected at Screening, Baseline, Month 3, Month 6, Month 9 and Month 12 according to the Schedule of Activities in Section 9 of the protocol.

Z-scores include height standard deviation score (SDS) by chronologic age, height SDS by bone age, weight SDS by chronologic age, weight SDS by bone age. Z-scores will be calculated by the sponsor using SAS macros following World Health Organization (WHO) reference standards. The input variable of age will be repeatedly applied using chronologic age and bone age in order to derive the above four SDS. Detailed documents on how the physical growth curves and motor milestone windows of achievement were developed as well as application tools to support implementation of the standards is publicly available at WHO website¹ for children ages 0-5 years and for children ages 5-19 years separately. Height SDS and Weight SDS should be calculated using the Statistical Analysis System (SAS) macros available at the same website.¹

There are no WHO reference standards for weight SDS for pediatric participants >10 years of age. Therefore, as an alternative, weight SDS for all pediatric participants will be also calculated using the CDC reference standards² and SAS programs.

In calculation of the percentage change from baseline for SDS, the absolute value of the baseline will be used as the denominator to address the situation where the value is negative.

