3.3.4. Modified Severity Scoring Tool (mSST)

Modified Severity Scoring Tool (mSST) will be collected at Screening, Month 6 and Month 12 according to the Schedule of Activities in Section 9 of the protocol. The total score is a sum of the single scores from gaze palsy, ophthalmology, epilepsy, age at first epilepsy, cognitive ability, ataxia of gait, cerebellar tremor, pyramidal, extrapyramidal, swallowing difficulties/oral bulbar function, speech and spinal alignment. It ranges from 0 to 36, while 0 indicating normal and 36 indicating severe symptom.

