6.3. Other Secondary Endpoints

- Estimand strategy: Treatment policy strategy for change from baseline in height SDS, weight SDS, tanner stage, bone age, BMD and Z-score for bone assessment, total score from mSST, as well as change from baseline in organ volume measured by ultrasound if available.
- Analysis set: FAS (defined in [Section 4](#)). All participants assigned to study drug and who take at least 1 complete dose of taliglucerase alfa (or partial dose if adverse events prevent completing infusion dose).
- Intercurrent events and missing data: Data after study drug discontinuation will be excluded; Missing values won't be included in calculating change from baseline and will not be imputed.
- Descriptive statistics including n, mean, SD, median, minimum, and maximum will be presented for observed continuous variables at each visit. This includes the absolute values, change from baseline and percent change from baseline in height SDS by chronologic age, height SDS by bone age, weight SDS by chronologic age, weight SDS by bone age, bone age, BMD and Z-score for bone assessment, right and left testis volume, total score from mSST, and spleen volume, spleen volume MN, liver volume, liver volume MN measured by ultrasound.

- BDM and Z-score for bone assessment will be descriptively summarized by each bone area, such as L femoral neck, total left hip, total body, etc. that listed in [Section 3.3.3](#).
- Frequency and percentage will be provided for categorical variables at each visit, such as tanner stage.

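### SAP 6.3 tabulates percent change for height/weight SDS, DEXA Z-score and mSST, scales on which percent change is not meaningful; the effect is confined to descriptive tables.

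*SAP*

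**What the plan says.** SAP section 3 sets the general rule: "Percent change from baseline will be calculated at the participant level", as post-baseline minus baseline, divided by baseline with its sign, times 100.

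SAP 3.3.1 (Height SDS and Weight SDS) makes one exception, for SDS: "the absolute value of the baseline will be used as the denominator". Its stated purpose is to deal with negative baselines.

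The descriptive-statistics bullet in SAP 6.3 then lists what is tabulated with n, mean, SD, median, minimum and maximum: "This includes the absolute values, change from baseline and percent change from baseline in height SDS by chronologic age, height SDS by bone age". The same list continues with the two weight SDS variables and "bone age, BMD and Z-score for bone assessment, right and left testis volume, total score from mSST".

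On the mSST, SAP 3.3.4 says: "It ranges from 0 to 36, while 0 indicating normal and 36 indicating severe symptom". SAP 3.3.3 collects the DEXA Z-score at seven bone areas and gives no denominator rule.

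Elsewhere only change is named. Protocol 8.1 lists change in height SDS, weight SDS, bone mineral density and mSST. Protocol 10.3.4 adds change in the bone Z-score. SAP Appendix 1 and the estimand bullet of SAP 6.3 also speak of change for these variables. Percent change for them appears only in the SAP 6.3 descriptive bullet and the SAP 3.3.1 denominator sentence.

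**The concern.** Percent change needs a scale whose zero means none of the quantity, and a baseline clear of that zero. An SDS or Z-score of 0 is the reference mean, an ordinary value that a child can have at baseline or cross during the year. The mSST is a summed severity score whose lowest value, 0, is a permitted baseline.

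Three different faults follow, each for its own variable:

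- **DEXA Z-score:** wrong sign whenever the baseline is negative, and very large values near 0.
- **Height and weight SDS:** very large values near 0, and no value at 0.
- **mSST:** no value at 0, and heavy dependence on the starting score elsewhere.

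At stake is whether a reader of the study report can trust these table columns. In a single-arm trial of up to 15 subjects, one subject can set the mean and SD of such a column.

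**Working it through.** The plan states no figure on this point, so there is none to reproduce. The documents also give no SDS, Z-score or mSST data. Every baseline below is therefore an assumption, chosen to show how the formulas behave.

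**Inputs from the documents**

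- Signed formula (SAP section 3): 100 × (post − base) / base.
- Absolute-denominator formula (SAP 3.3.1, SDS only): 100 × (post − base) / |base|.
- mSST range 0 to 36, with 0 normal (SAP 3.3.4).
- Protocol 6.3.1 and 6.3.2 set no minimum mSST.
- Up to 15 enrolled, to yield at least 9 completers (protocol synopsis).

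**1. DEXA Z-score, signed formula**

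- −2 to −1, an improvement: 100 × (1) / (−2) = −50%.
- −2 to −1.7, an improvement: 100 × (0.3) / (−2) = −15%.
- −0.1 to +0.2, an improvement: 100 × (0.3) / (−0.1) = −300%.

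**2. Height or weight SDS, absolute denominator, same gain of 0.3 SD throughout**

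| Baseline | Percent change |
|---|---|
| −3 | 100 × 0.3 / 3 = +10% |
| −1 | 100 × 0.3 / 1 = +30% |
| −0.1 | 100 × 0.3 / 0.1 = +300% |
| −0.05 | 100 × 0.3 / 0.05 = +600% |
| 0 | undefined |

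The sign is right in every row with a value; the size depends almost wholly on the baseline.

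**3. mSST, signed formula, same one-point worsening**

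- 0 to 1: undefined.
- 1 to 2: +100%.
- 10 to 11: +10%.
- 20 to 21: +5%.

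**4. One near-zero baseline among nine subjects**

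Take nine SDS baselines of −3, −2.5, −2.2, −2, −1.8, −1.5, −1.2, −1 and −0.05, with every subject gaining exactly 0.3. The percent changes are 10, 12, 13.6, 15, 16.7, 20, 25, 30 and 600.

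- All nine: mean 82.5%, SD 194, median 16.7%.
- Without the last subject: mean 17.8%, SD 6.8.
- Absolute change: +0.3 for every subject.

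**5. How likely is a near-zero SDS baseline?**

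Assume normal baselines with mean μ and SD 1. The chance that one subject has |SDS| < 0.1 is q = Φ(0.1 − μ) − Φ(−0.1 − μ). The chance of at least one among n subjects is 1 − (1 − q)^n.

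| Assumed μ | q | n = 9 | n = 15 |
|---|---|---|---|
| −2 | 0.0109 | 9.4% | 15.1% |
| −1 | 0.0484 | 36.0% | 52.5% |
| 0 | 0.0797 | 52.6% | 71.2% |

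**The case against.** The strongest reply is that nothing the protocol asks for is lost. The sentence in SAP 6.3 that plans percent change also plans the absolute value and the absolute change, so percent change is one extra column. The tables also show the median, minimum and maximum: in step 4 the median stays at 16.7% and the maximum exposes the outlier. These endpoints carry no test, imputation or decision rule. The SAP introduction allows the SAP to modify the protocol's plans, so an added descriptive column is not a breach of the protocol. All of this stands, and it is why the point is minor.

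Two stronger readings are tempting and not supported.

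- A reader might infer that the SAP 3.3.1 rule gives wrong-signed results for height and weight SDS. It does not; dividing by |baseline| makes every gain positive. Wrong sign is confined to the DEXA Z-score. One could argue that the rule reaches that variable too, because SAP 3.3.1 treats SDS and Z-score as interchangeable terms. But that section concerns height and weight, and the DEXA Z-score is defined separately in SAP 3.3.3. Even if the rule did reach it, the near-zero problem would remain.
- A reader might infer that subjects with an mSST of 0 drop out of the mSST analysis. They would be missing only from the percent-change column and remain in the absolute-value and change summaries.

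Nor is an mSST of 0 shown to be common. The documents define Type 3 disease by primary nervous-system involvement, and the mSST scores neurological items. The fair claim is that a score of 0 is allowed and no rule covers it.

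**Conclusion.** The point holds as a minor one. Percent change is not meaningful for height and weight SDS, the DEXA Z-score or the mSST total, and the planned formulas could print misleading or missing values.

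The sign reversal for the DEXA Z-score needs only a negative baseline, on the reading that the SAP 3.3.1 exception does not cover it. The very large SDS values and the missing mSST values depend on who enrols. Under the assumed distributions, the chance of at least one SDS baseline within 0.1 of zero runs from 9.4% (mean −2, nine subjects) to 71.2% (mean 0, fifteen subjects).

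A reader might go on to infer that the efficacy conclusions are at risk. They are not: the primary and secondary tests, the responder analysis and the sample size use none of these quantities.

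**What to change.** In the descriptive-statistics bullet of SAP 6.3, remove percent change for the four height and weight SDS variables, the DEXA Z-score and the mSST total. Keep the absolute value and absolute change already planned there, which match protocol 8.1 and 10.3.4 and SAP Appendix 1. Delete the denominator sentence in SAP 3.3.1, which would then have no use. Percent change for BMD itself may stay, because BMD is a positive quantity with a true zero.

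With absolute change only, a gain of 0.3 SD reads +0.3 from any baseline, including 0, and an mSST move from 0 to 1 reads +1.

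The cost is a short SAP wording edit and fewer table columns. No data collection, endpoint or analysis set changes.

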3.3.2. Tanner Stage

Tanner stage of development will be collected at Baseline and Month 12 according to the Schedule of Activities in Section 9 of the protocol, including pubic hair stage (stage 1 to 5), genitalia stage (stage 1 to 5) and testis volume (mL).

3.3.3. Bone Measurement

Bone age assessed by X-ray of left hand and wrist will be collected at Baseline and Month 12 according to the Schedule of Activities in Section 9 of the protocol.

Bone mineral density (BMD) and Z-score assessed by dual-emission X-ray absorptiometry (DEXA) for L femoral neck, total left hip, R femoral neck, total right hip, lumbar spine, cortical bone and total body will be collected at baseline and Month 12 according to the Schedule of Activities in Section 9 of the protocol. The DEXA will be done in children 9 years of age and above.

3.3.4. Modified Severity Scoring Tool (mSST)

Modified Severity Scoring Tool (mSST) will be collected at Screening, Month 6 and Month 12 according to the Schedule of Activities in Section 9 of the protocol. The total score is a sum of the single scores from gaze palsy, ophthalmology, epilepsy, age at first epilepsy, cognitive ability, ataxia of gait, cerebellar tremor, pyramidal, extrapyramidal, swallowing difficulties/oral bulbar function, speech and spinal alignment. It ranges from 0 to 36, while 0 indicating normal and 36 indicating severe symptom.

3.3.5. Organ Volumes measured by Ultrasound

Spleen volume and liver volume will be also measured by ultrasound at the Screening, Month 6 and Month 12 according to the Schedule of Activities in Section 9 of the protocol. If collected, the spleen volume and liver volume will be calculated as the product of craniocaudal dimension (cm), anteroposterior dimension (cm) and longitudinal dimension (cm) from ultrasound measurement.

The spleen volume by MN will be calculated by sponsor applying the formula in [Section 3.1](#) based on the spleen volume (cm³) measurement by ultrasound and body weight. The liver volume by MN will be calculated by sponsor applying the formula in [Section 3.2.1](#) based on the liver volume (cm³) measurement by ultrasound and body weight.

3.4. Baseline Variables

Baseline is defined as Screening visit (Visit 0) for spleen volume defined in [Section 3.1](#), liver volume defined in [Section 3.2.1](#) and mSST defined in [Section 3.3.4](#). Baseline is defined as Day 1 (or Visit 1) for the endpoints specified in [Sections 3.2.2 to 3.3](#), which are corresponding to the secondary efficacy assessment, growth development, biomarker measurement, as well as the adverse events in [Section 3.5](#) for the safety assessment.

3.5. Safety Endpoints

3.5.1. Adverse Events

The adverse event (AE) including time of the onset, severity, action/treatment and outcome of the AE resolution, related to taliglucerase alfa treatment or not, will be collected at each scheduled visit with the visit window specified in the Schedule of Activities in Section 9 of the protocol.

An AE is considered as a treatment emergent adverse event (TEAE), if the event occurring or worsening on or after the first dose of taliglucerase alfa in the study. The AE reporting period for this study will be defined as the duration from the first dose of taliglucerase alfa in the study until 30 calendar days following the final visit dose.

3.5.2. Laboratory Data

Lab data other than hemoglobin and platelet counts will be collected at Screening, baseline, Month 3, Month 6, Month 9 and Month 12 according to the Schedule of Activities in Section 9 of the protocol, including hematology, biochemistry and urinalysis lab tests.

3.5.3. Vital Signs

Vital sign data will be collected during each bi-weekly Taliglucerase alfa infusion. It will be evaluated every 30 minutes if the participant tolerates the previous infusions; otherwise, every 15 minutes for the first hour.

3.5.4. Antibodies

Anti-taliglucerase alfa antibodies will be collected at baseline, Month 6 and Month 12 according to the Schedule of Activities in Section 9 of the protocol, including the status (positive, negative, not done) for IgG, in-vitro neutralizing, cell based neutralizing, and IgE anti-taliglucerase alfa antibodies.

4. ANALYSIS SETS (POPULATIONS FOR ANALYSIS)

Data for all participants will be assessed to determine if participants meet the criteria for inclusion in each analysis population prior to releasing the database and classifications will be documented per standard operating procedures.

The analysis populations for reporting are defined in the following table.

Population	Description
Enrolled	All participants who sign the informed consent document.
Evaluable or Full Analysis Set (FAS)	All enrolled participants to the study who take at least 1 complete dose of taliglucerase alfa (or partial dose if adverse events prevent completing infusion dose). Participants will be collected according to the study drug actually received for this non-randomized study.
Safety	All participants who receive at least 1 dose of study drug. Participants will be analyzed according to the study drug they actually received. An enrolled but not treated participant will be excluded from the safety analyses.
Per Protocol set (PP)	All participants who complete the primary efficacy data collection at Month 12 and baseline assessment, and receive at least 1 complete dose of taliglucerase alfa (or partial dose if adverse events prevent completing infusion dose).

5. GENERAL METHODOLOGY AND CONVENTIONS

5.1. Hypotheses and Decision Rules

For the primary efficacy endpoint, a Wilcoxon signed rank test at 2-sided significance level of 0.05 will be applied to test the null hypothesis that the median percent change from baseline to Month 12 in spleen volume MN is equal to -20%. The corresponding p-value will be reported.

The primary null hypothesis is:

$$H_0: \lambda = -20\%$$

and the primary alternative hypotheses are:

$$H_{a1}: \lambda < -20\% \text{ and } H_{a2}: \lambda > -20\%,$$

where λ is the common median of the observed percent difference from the paired data.

Taliglucerase alfa will be considered efficacious with respect to the spleen volume MN, if the median percent change from baseline to Month 12 is significantly less than -20% (or the median percent reduction is greater than 20%) at the 2-sided 0.05 level, ie, p-value from Wilcoxon signed rank test less than 0.05.

For the secondary efficacy endpoints, such as hemoglobin, platelet counts and Lyso-Gb1, the same Wilcoxon signed rank test will be applied for the percent change from baseline to Month 12. No adjustment for multiple comparisons will be made. Though hemoglobin, platelet counts, chitotriosidase and Lyso-Gb1 will be collected at Month 3, 6 and 9 as well, changes from baseline to Months 3, 6 and 9 will be descriptively summarized only.

5.2. General Methods

5.2.1. Analyses for Binary Endpoints

Frequency and percentage of the responders defined in [Section 2.1.3](#), will be provided as a descriptive type of summary. The 95% confidence interval for the responder rate will be provided using exact Clopper-Pearson method via one sample procedure in SAS Proc Freq. The sample code is provided in [Appendix 4](#).

5.2.2. Analyses for Continuous Endpoints

The Wilcoxon signed rank test will be performed for the percent change from baseline to Month 12 in primary and secondary efficacy endpoints due to the possible skewed distribution for the efficacy data.

The rank with positive and negative signs will be assigned to the percent difference (D_i) between baseline and Month 12 values. D_i are a random variable, which are mutually independent from each participant and have the same median. All the zero differences are ignored in the analysis. The Wilcoxon signed rank test inference is based on permutational distribution of its test statistics. This test will be implemented and exact p-values will be produced via SAS Proc Univariate. The Proc Univariate excludes missing values for an analysis variable before calculating statistics. The sample code is provided in [Appendix 4](#).

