5.3. Methods to Manage Missing Data

The missing data for the primary and secondary efficacy endpoints analyzed by the Wilcoxon signed rank test will be imputed using last observation carried forward (LOCF) method in FAS, ie, the measurement obtained at the early termination visit will be used to impute the Month 12 data.

For imaging-based endpoints, the spleen volume and liver volume measured by the MRI at the early termination visit will be taken as the Month 12 measurement, if the Month 12 visit is missing. If there is no post-baseline MRI measurement, the percentage change from baseline to Month 12 in organ volumes by ultrasound can be used to impute the missing percentage change from baseline in organ volumes by MRI per clinical judgment. The percentage change from baseline needs to be derived within the same imaging test, ie, based on post-baseline organ volume measured by ultrasound and baseline organ volume measured by ultrasound. If there is no post-baseline imaging measurement, the baseline observation carried forward (BOCF) will be applied for missing data, ie, the baseline volume measured by MRI will be used to impute Month 12 MRI data.

Missing safety data will be handled according to the Pfizer Clinical Data Interchange Standards Consortium (CDISC) safety rulebook and data standard rules for imputation, including missing dates (when the date is required for a calculation) and missing severity of adverse events.

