6.2. Key Secondary Endpoints

6.2.1. Main Analysis

- Estimand strategy: Treatment policy strategy for percent change from baseline to Month 12 in liver volume MN measured by MRI, hemoglobin, platelet and Lyso-Gb1 (lyso-glucosylsphingosine), chitotriosidase.
- Analysis set: FAS (defined in [Section 4](#)). All participants assigned to study drug and received at least 1 complete dose of taliglucerase alfa (or partial dose if adverse events prevent completing infusion dose) will be included.

- Analysis methodology: Percent change from baseline to Month 12 will be analyzed using Wilcoxon signed rank test detailed in [Section 5.2.2](#).
- Intercurrent events and missing data: Data after study drug discontinuation will be included; Missing values will be imputed using LOCF, and other methods specified in [Section 5.3](#), and included in calculating percent change from baseline.
- Summary of statistical comparison: The 2-sided p-value from the exact inference for Wilcoxon signed rank statistics for comparing Month 12 to baseline value, as well as median percent change from baseline, will be presented. The n, minimum and maximum for observed percent change from baseline will be presented together as well.
- Descriptive summary including n, mean, SD, median, minimum, and maximum for absolute value, change from baseline and percent change from baseline at each visit will be presented. The visit includes baseline and Month 12 for liver volume and liver volume MN measured by MRI, and baseline, Month 3, 6, 9 and 12 for hemoglobin, platelet, chitotriosidase and Lyso-Gb1.

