Appendix 4. Statistical Methodology Details

1. Sample code for Wilcoxon signed rank test:

```

data one;
  input id $ pre post;
  label pre='Baseline' post='Mon12';
  cards;
1    8.74  4.22
2    6.77
4    1.34  1.95
5    4.52  3.76
6    6.72  5.85
7    2.37  2.74
8    3.69  2.93
9    4.55  3.62
10   17.12 16.84
11   14.93 18.07
;run;
data two;
  set one;
  pctch=((post-pre)/pre)*100;
  adjpctch=pctch + 20;  ** for primary efficacy endpoint **;
run;

** Wilcoxon signed rank test for primary efficacy endpoint with decision
criteria;
proc univariate data=two;
  var adjpctch;
  output out=rankpct SIGNRANK=statistics PROBS=p median=median;
run;

** Wilcoxon signed rank test for secondary efficacy endpoints;
proc univariate data=two;
  var pctch;
  output out=rankpct SIGNRANK=statistics PROBS=p median=median;
run;

```

2. Sample code for Clopper-Pearson exact test and CI for the responder rate:

```

data three;
  input status $ count;
  cards;
  respond 8
  nonresp 1;
run;
proc freq data=three;
  table status/binomial (exact p=0.5) alpha=0.05;
  weight count;
run;

```

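### For liver volume MN, a participant imputed by BOCF at exactly zero change is dropped from the signed rank test, so that imputation does not affect the liver p-value

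*SAP*

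**What the plan says.** SAP 5.3 deals with a missing Month 12 organ volume in three steps.

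1. If an early termination scan exists, "the spleen volume and liver volume measured by the MRI at the early termination visit will be taken as the Month 12 measurement".
2. If there is no post-baseline MRI, the percent change "in organ volumes by ultrasound can be used to impute the missing percentage change from baseline in organ volumes by MRI per clinical judgment".
3. "If there is no post-baseline imaging measurement, the baseline observation carried forward (BOCF) will be applied for missing data"; that is, "the baseline volume measured by MRI will be used to impute Month 12 MRI data".

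SAP 6.2.1 applies this to liver volume MN in the FAS: "Missing values will be imputed using LOCF, and other methods specified in" Section 5.3, with the imputed values included when percent change is calculated. It adds: "The n, minimum and maximum for observed percent change from baseline will be presented together as well".

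SAP 5.2.2 describes the test and states: "All the zero differences are ignored in the analysis". In SAP Appendix 4, the code block labelled "Wilcoxon signed rank test for secondary efficacy endpoints" analyses the unshifted percent change. Only the primary endpoint has 20 points added first (SAP 6.1.1 and Appendix 4). SAP 6.2.2 plans no sensitivity or supplementary analysis for liver.

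**The concern.** The purpose of imputing in the FAS is that participants without a Month 12 value still contribute to the analysis. For the liver test, the last imputation step and the zero rule work against each other: BOCF supplies a zero and the test discards it. The p-value labelled as FAS with imputation is then, for these participants, a scanned-only p-value. With no liver sensitivity analysis planned, no other liver result would show this.

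The reporting hides it further. The median is produced from the same variable and includes the zeros, the p-value excludes them, and the n, minimum and maximum are for observed changes. One table line can therefore describe different sets of participants.

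**Working it through.** **Inputs.** BOCF only when there is no post-baseline imaging (SAP 5.3). Zeros ignored (SAP 5.2.2). Null of 0% for liver and -20% for spleen (SAP 5.1, 6.1.1, Appendix 4). Nine evaluable subjects (Protocol 10.1). Up to 15 enrolled to yield at least 9 completers, hence at most 15 - 9 = 6 non-completers if nine complete (Protocol synopsis). The patterns of change below are illustrative.

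**The plan's own figure.** The documents give no power or p-value for liver. The spleen calculation reproduces: a two-sided sign test with n = 9, rejecting at 8 or more or 1 or fewer responders, has alpha = 2 x (9 + 1)/512 = 0.039 (stated 0.04) and power 0.8088 at a responder rate of 0.91 (stated 80.9%).

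**Step 1: the same zero in the two tests.** Spleen: 0 + 20 = +20, a positive value that is ranked and counts against the drug. For example, eight completers at -25% to -46% plus one BOCF participant give n = 9 and p = 0.0586. Liver: 0 stays 0 and is removed. Proc Univariate also excludes missing values, so the liver p-value is the same as with no imputation.

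**Step 2: nine scanned, all improved, plus k BOCF zeros.**
- Dropped (SAP rule): p = 2/2^9 = 0.0039 for every k.
- Kept as the lowest-ranked adverse values: the zeros share mid-rank (k + 1)/2, so the adverse rank sum is k(k + 1)/2, and p = 2 x (number of sign patterns with a rank sum no larger)/2^(9 + k).

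| k | adverse rank sum | patterns | p, zeros kept | p, zeros dropped |
|---|---|---|---|---|
| 1 | 1 | 2 of 1024 | 0.0039 | 0.0039 |
| 2 | 3 | 5 of 2048 | 0.0049 | 0.0039 |
| 4 | 10 | 40 of 8192 | 0.0098 | 0.0039 |
| 6 | 21 | 382 of 32768 | 0.0233 | 0.0039 |

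**Step 3: FAS of nine, k unscanned, all scanned improved.** Dropped: p = 2/2^(9 - k).

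| k | p, zeros dropped | p, zeros kept |
|---|---|---|
| 1 | 0.0078 | 0.0078 |
| 2 | 0.0156 | 0.0195 |
| 3 | 0.0313 | 0.0547 (2 x 14/512) |
| 4 | 0.0625 | 0.1523 |

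At k = 3 the two treatments fall on opposite sides of 0.05.

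**Step 4: the median.** With six completers at -5, -7, -9, -11, -13 and -15%, the median is -10%. Adding three zeros moves it to -7%, while the p-value still rests on the six.

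**Step 5: is the imputed change really zero?** Liver MN = volume/(25 x body weight), and a missing weight is replaced by the previous visit's (SAP 3.2.1). If only the cm3 volume is carried and weight has changed by a fraction g, the imputed change is (1/(1 + g) - 1) x 100. An assumed g = +0.10 gives -9.1%, scored as improvement. An assumed g = -0.05 gives +5.3%, scored as worsening. The SAP does not say which applies.

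**The case against.** Dropping zeros is a usual signed rank convention and is openly prespecified. BOCF is a last resort: the protocol asks for the Month 12 procedures, including MRI, at early termination (Protocol 6.3.3, 9.2.12) and schedules ultrasound at Month 6, so few participants may reach it. Liver is a secondary endpoint with no success rule; the efficacy criterion concerns spleen alone. All of this stands and limits the weight of the point.

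A reader might infer that liver non-completers can never count against the drug. The documents do not support that. Those with an early termination MRI, or an ultrasound change accepted on clinical judgment, enter with that value whatever its direction. BOCF zeros pull the median toward 0. In a FAS of fixed size they lower the number tested and so raise the smallest attainable p, although leaving the values missing would cost the test just as much. If volume alone is carried and weight has fallen, the imputed change is adverse.

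Nor does the SAP call the liver imputation conservative. It says only that imputed values are included in calculating percent change, and a BOCF zero is included in that sense.

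A reader might also gauge the effect with an exact sign test that scores BOCF participants as not improved. With nine improved, 9/10, 9/11, 9/13 and 9/15 give p = 0.021, 0.065, 0.27 and 0.61. Most of that rise comes from changing the test: keeping the signed rank test gives 0.0039, 0.0049, 0.0098 and 0.0233. The last case also needs all six non-completers to lack any usable imaging.

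**Conclusion.** The point holds within limits. When BOCF gives exactly 0% change in liver MN, the imputation stated for the FAS does nothing to the liver p-value, although it shifts the median printed beside it. The same imputation is effective for spleen, and the SAP does not remark on the difference.

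The size is modest. With nine scanned and all improved, one or two zeros barely matter and even six leave p at 0.0233. In a FAS of nine with three unscanned and six improved, p is 0.031 with zeros dropped and 0.055 with zeros kept.

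These figures assume that all scanned participants improve and that BOCF participants are ranked lowest and adverse. The zero itself assumes that MN, or volume with an unchanged weight, is carried forward, which the SAP leaves open. The primary spleen test is not touched by the zero rule in this way.

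**What to change.** - **SAP 5.3:** state that under BOCF the baseline MN (volume and weight together) is carried forward, so the imputed liver change is exactly zero.
- **SAP 6.2.1 and 6.2.2:** add a liver sensitivity analysis in the whole FAS that keeps BOCF participants as not improved. This can be a signed rank test with the zeros ranked lowest and adverse, an exact sign test, or both. If both are reported, note that the sign test is the stricter in the cases shown.
- **Liver results table:** print the numbers tested, imputed and dropped as zeros beside the median and p-value.

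The cost is SAP wording, a little extra programming, and a liver p-value that may be less favourable. No additional data are needed.
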